6.1.1. Local Reactions

Within each study stage, the local reactions assessed and reported in the e-diary are redness, swelling, and pain at the injection site, from Day 1 to Day 14 following vaccination, where Day 1 is the day of vaccination.

Subjects will record presence or absence of redness and swelling. If present, the reaction will be measured and recorded in measuring device units (range: 1 to 21+). Measuring device units can be converted to centimeters according to the following scale: 1 measuring device unit = 0.5 cm. The reaction will be categorized for analysis as mild, moderate, or severe based on the grading scale in [Table 1](#) below. Redness or swelling less than 2.5 cm will be assigned as “none,” but such values will still be reported in the listings.

Pain at the vaccine injection site will be assessed by the subject as mild, moderate, or severe according to the grading scale in [Table 1](#).

Note that Grade 4 severities will not be collected in the e-diary but will be collected as AEs on the case report form (CRF). Grade 4 will not be analyzed as part of local reactions.

For each local reaction, the maximum severity grade of the reaction based on the severity grading scale of the local reactions in [Table 1](#) will be derived for the e-diary collection period (Day 1 to Day 14, where Day 1 is the day of vaccination) as follows:

= missing, if all values are missing for Day 1 to Day 14;

= 0 (or none), if the subject reports all reactions as “no” or a combination of missing and “no” for all Days 1 to 14 or (redness and swelling only) if the largest diameter is <5 measuring device units (ie, <2.5 cm);

= highest grade (maximum severity) within 14 days after vaccination (Day 1 to Day 14) among severity grades where the answer is not “no” for at least 1 day during Days 1 to 14.

Table 1. Grading Scales for Local Reactions

	Mild Grade 1	Moderate Grade 2	Severe Grade 3	Grade 4
Redness (erythema)	5 to 10 measuring device units = 2.5 to 5.0 cm	11 to 20 measuring device units = 5.5 to 10.0 cm	≥ 21 measuring device units = ≥ 10.5 cm	Necrosis or exfoliative dermatitis
Swelling (edema)	5 to 10 measuring device units = 2.5 to 5.0 cm	11 to 20 measuring device units = 5.5 to 10.0 cm	≥ 21 measuring device units = ≥ 10.5 cm	Necrosis
Pain at injection site	Does not interfere with activity	Interferes with activity	Prevents daily activity	Emergency room visit or hospitalization

Abbreviation: e-diary = electronic diary.

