Note: If the size of the redness and/or swelling falls between 2 measuring device units, the higher measuring device unit number will be recorded in the e-diary.

Presence or Absence

For the data summary of the presence (yes or no) of a local reaction during Day 1 to Day 14 following vaccination, where Day 1 is the day of vaccination, the following variables are required:

- Maximum severity of each local reaction on any day (Day 1 to Day 14);
- Presence (yes or no) of each local reaction on each day (Day 1 to Day 14);
- Presence (yes or no) of each local reaction on any day (Day 1 to Day 14);
- Presence (yes or no) of any local reaction on each day (Day 1 to Day 14);
- Presence (yes or no) of any local reaction on any day (Day 1 to Day 14);
- Presence (yes or no) of each severe (Grade 3) (as defined in Table 1) local reaction on each day and any day (Day 1 to Day 14);
- Duration of each local reaction (duration will be calculated both from the first to the last day and also as total days with the indicated event);
- Onset day of each local reaction;

C [REDACTED].

For each local reaction, Table 2 below explains the algorithm to derive the presence of a reaction (yes or no) during Day 1 to Day 14 following vaccination, where Day 1 is the day of vaccination.

Table 2. Derived Variables for Each Local Reaction Within the Time Interval

Variable ^a	Yes (1)	No (0)	Missing (.)
Any Day 1 to 14	Subject reports the reaction as present (“yes”) on any Day 1 to 14. For redness and swelling this includes any nonzero measurement.	Subject reports the reaction as “no” on all 14 Days 1 to 14 or as a combination of “no” and missing on all 14 Days 1 to 14.	Reaction data are missing on all 14 Days 1 to 14.

- a. The variable will be derived for each of the local reactions (redness, swelling, pain at the injection site) and also for each of the severe local reactions within Day 1 to Day 14 following vaccination.

For any local reaction on any day, a similar rule applies as specified below in Table 3:

Table 3. Derived Variables for Any Local Reaction Within the Time Interval

Variable ^a	Yes (1)	No (0)	Missing (.)
Any Day 1 to 14	Subject reports “yes” or “mild” or greater for any local reaction on any Day 1 to 14.	Subject reports “no” on all 14 Days 1 to 14 or as a combination of “no” and missing on all 14 Days 1 to 14 on all 3 local reactions.	All 3 local reaction values are missing on all 14 Days 1 to 14.

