- a. The variable will be derived for any local reaction (any redness, swelling, pain at the injection site) and also for any severe local reaction within Day 1 to Day 14 following vaccination.

Duration (From First Day to Last Day Reported)

The duration of each local reaction will be calculated as the number of days from the start of the first reported reaction to the resolution of the last reported reaction, inclusive. Days with redness or swelling with diameter <2.5 cm will be excluded. Resolution is the last day on which the reaction is recorded in the e-diary if the reaction lasted 14 days or less, or the date the reaction ended if it continued beyond Day 14 (the latter will be collected on the CRF). If there is no known date when the reaction ended, then duration will be missing (unknown). Subjects with no reported reaction have no duration because it is not applicable.

Duration of reactions ≥ 21 measuring device units will also be compiled.

Duration (Total Days Reported)

The duration (total days) of each local reaction will be calculated as the number of days with the reported reaction, including days after Day 14 (if any). Days with redness or swelling with diameter <2.5 cm will be excluded.

If there is no known date when the reaction ended, then duration (total days) will be missing (unknown). Subjects with no reported reaction have no duration because it is not applicable.

Total days of reactions ≥ 21 measuring device units will also be compiled.

Onset

The onset day of each local reaction and any local reaction will be derived. Days with redness or swelling with diameter < 2.5 cm will be excluded.

For the onset day of each local reaction, if subjects report severity change of the local reaction, only the first day of reporting that specific local reaction will be counted.

For the onset day of any local reaction, the first day of reporting any severity of any local reaction will be counted.

CCI

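### SAP 6.1.1 grades redness and swelling under 2.5 cm as none, and omits them from onset and duration, but Table 2 counts them as present

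*SAP*

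**What the plan says.** All of the conflicting text is in SAP Section 6.1.1.

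- **Recording.** "Subjects will record presence or absence of redness and swelling". If present, the size is entered in units from 1 to 21+, where 1 unit is 0.5 cm. Entries of 1 to 4 units are therefore possible.
- **General rule.** "Redness or swelling less than 2.5 cm will be assigned as" none. Such values are kept in the listings. The sentence is not limited to severity.
- **Maximum severity.** Grade 0 applies, for redness and swelling, "if the largest diameter is <5 measuring device units". Table 1 starts Grade 1 at 5 units.
- **Onset and both duration definitions.** "Days with redness or swelling with diameter <2.5 cm will be excluded".
- **Presence of each reaction (Table 2).** Yes is a reported reaction on any of Days 1 to 14. "For redness and swelling this includes any nonzero measurement". No requires a reported no on every day, or no combined with missing.
- **Presence of any reaction (Table 3).** "For any local reaction on any day, a similar rule applies as specified below in Table 3". Its Yes cell accepts a reported yes, or mild "or greater for any local reaction on any Day 1 to 14".
- **Severe reactions.** Footnote a of Tables 2 and 3 extends both tables to severe reactions. The variable list in the same section refers to Grade 3 in Table 1.

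SAP Section 8.2.1.1 summarizes both presence and maximum severity as proportions with exact confidence intervals. Protocol Section 7.2.3.1 records units from 1 and then grades them, with no category below 5 units. Protocol Section 9.4 presents local reactions by severity and cumulatively over severity levels.

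**The concern.** Two rules for the same recorded value disagree, and no order of derivation is stated. A 1-to-4-unit entry is none under the general, severity, onset and duration rules, but Yes under Table 2. It cannot fall into Table 2's No cell, because the subject did not report no.

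The proportions with redness and with swelling within 14 days are primary endpoints in both stages (SAP Section 6.1). Two programmers working from this text could produce different primary tables. If Table 2 is followed, a reader will find more subjects with redness than the three grades add up to. Some of those subjects will have no onset day or duration, although the SAP makes duration not applicable only for subjects with no reported reaction. The bar charts by day in Section 8.2.1.1 are split by severity, so if daily presence follows Table 2 these subjects have no severity segment.

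Table 3 and the daily presence variables are ambiguous and not contradictory: the general none rule could govern them, but Table 2's wording points the other way. Pain is unaffected.

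**Working it through.** **1. The plan's own threshold.** At 0.5 cm per unit (SAP 6.1.1), 5 × 0.5 = 2.5 cm, so the two statements of the cut-off agree. Values of 1, 2, 3 and 4 units are 0.5, 1.0, 1.5 and 2.0 cm.

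**2. The rules applied to each possible largest value.**

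| Largest value (units) | Maximum severity | Table 2 presence | Onset and duration |
|---|---|---|---|
| 0 | none | No | none |
| 1–4 | none | **Yes** | none |
| 5–10 | mild | Yes | derived |
| 11–20 | moderate | Yes | derived |
| 21 or more | severe | Yes | derived |

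The rules disagree only at 1 to 4 units. With a 5-unit floor in Table 2 they agree at every value.

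**3. Two test diaries.**

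- Units 0, 1, 4, 3, then 0 to Day 14: severity none, Table 2 presence Yes, no onset, no duration.
- Units 2, 4, 6, 5, 3, then 0 to Day 14: mild, present, onset Day 3, duration 2 days. Table 2 applied day by day would show a reaction on Days 1 to 5.

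**4. Effect per subject.** Protocol Section 9.1 plans about 33 randomized per group in Stage 1 and 220 in Stage 2, with about 30 and 200 evaluable. A subject whose only redness (or only swelling) is 1 to 4 units adds 1/n to that presence proportion:

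- Stage 1: 1/33 = 3.03 points, or 1/30 = 3.33.
- Stage 2: 1/220 = 0.45 points, or 1/200 = 0.50.

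The smaller denominators are shown because SAP Section 5.1 lets subjects without safety data be left out of an analysis.

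**5. Exact intervals.** The Clopper-Pearson formulas in SAP Section 8.1.1 are p_L = rF_L / (rF_L + n − r + 1) and p_U = (r + 1)F_U / (n − r + (r + 1)F_U). For r = 0 the upper limit reduces to 1 − 0.025^(1/n), which gives 1 − 0.025^(1/33) = 10.58% and 1 − 0.025^(1/220) = 1.66%.

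| r/n | Proportion | 95% CI |
|---|---|---|
| 0/33 | 0% | 0 to 10.58% |
| 1/33 | 3.03% | 0.08 to 15.76% |
| 0/220 | 0% | 0 to 1.66% |
| 1/220 | 0.45% | 0.01 to 2.51% |

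**6. How many subjects make a visible shift.** Taking 5 points as an illustrative benchmark (mine, not the plan's), 0.05 × 33 = 1.65, so 2 subjects are needed (2/33 = 6.06 points). In Stage 2, 0.05 × 220 = 11 subjects (5.00 points).

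**7. A range under assumed rates.** The documents give no rate of small marks. Suppose about 10% have graded redness and a further 5%, 10% or 20% have only 1 to 4 units, with counts rounded to whole subjects.

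| Stage | Graded | Table 2, +5% | Table 2, +10% | Table 2, +20% |
|---|---|---|---|---|
| 1 | 3/33 = 9.1% | 5/33 = 15.2% | 6/33 = 18.2% | 10/33 = 30.3% |
| 2 | 22/220 = 10.0% | 33/220 = 15.0% | 44/220 = 20.0% | 66/220 = 30.0% |

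**8. Severe variables.** Read on its own, Table 2's Yes cell would code 1 to 20 units as severe, and a bare 5-unit floor would still code 5 to 20 units as severe. Only an explicit reference to Grade 3 (21 units or more) gives the intended variable. Because the variable list already cites Table 1, this is a wording gap and not a second conflict. It does have to be handled when the floor is added.

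**The case against.** The strongest reply is that presence may be meant to be broader than grade. The endpoint is worded in terms of subjects reporting a reaction, Table 2 follows that wording, and presence and maximum severity are listed as separate variables. On that reading the two proportions are different quantities, and counting every mark is the more inclusive choice in a first-in-human study. The SAP's revision history shows that version 2.0 touched both the none sentence and the Table 2 sentence and left both standing. Parts of Section 6.1.1 are redacted. Naming a 2.5 cm floor for a primary endpoint might also raise the question of a protocol amendment, which Protocol Section 9 requires for major changes to primary endpoint definitions or analyses.

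Some of this stands. Intent cannot be read from the visible text, and an any-mark proportion is a legitimate thing to report. But nothing visible says that presence uses a different threshold, and the none sentence is unqualified. The only reason logged for the Table 2 edit was to remove the word caliper. The 5-unit floor is the section's own threshold for severity, onset and duration, and it fits both the remark that small values stay in the listings and the cumulative presentation in Protocol Section 9.4. Bringing a few cells into line with a rule the SAP already states is a clarification, not clearly a major modification.

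It also stands that the consequence is bounded. SAP Sections 4.1 and 4.2 exclude hypothesis tests and decision rules, the rule is the same in both arms, and the graded rates and listings remain available.

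**Conclusion.** The concern holds. As written, SAP 6.1.1 makes a subject with a largest mark of 1 to 4 units present for a primary endpoint while giving that subject severity none, no onset and no duration. That is an inconsistency between stated rules, not a missing detail, and it should be fixed before the tables are programmed.

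The conflict between the visible sentences is certain; its numerical effect is not. The per-subject figures assume the planned arm sizes, and the percentages in step 7 rest on assumed rates of small marks. If no subject has only 1 to 4 units, the 14-day presence proportions for redness and swelling do not change.

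**What to change.** - **Table 2.** For redness and swelling, make Yes require at least 5 units (2.5 cm), and count values under 5 units as no in the No cell.
- **Table 3.** Make Yes require mild or greater for any local reaction, and treat redness or swelling under 5 units as no.
- **Daily presence.** Add one sentence applying the same floor day by day.
- **Footnote a of both tables.** State that the severe variables use Grade 3 in Table 1 (at least 21 units for redness and swelling) in place of the 5-unit floor.
- **Unchanged.** The Missing cells and the listings.
- **If the sponsor also wants an any-mark proportion.** Define it as a separately labelled supportive variable and name the 2.5 cm version as the primary endpoint.

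The cost is four table cells, two footnotes, one sentence and the matching programming specification. No new data are needed. The downside is that reported redness and swelling presence rates may be lower than under Table 2 as written; the supportive variable would keep the any-mark rate visible. The sponsor should record briefly why it regards this as a clarification under Protocol Section 9.

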 - Remind the subject that study staff may assess him or her to obtain additional information on Grade 3 events entered into the e-diary.
 - Ask the subject to contact the investigator or site staff immediately if any significant illness or medical event (eg, emergency room visit or hospitalization) occurs during the study period.
 - Remind the subject to use appropriate contraceptives until 28 days after vaccination, if applicable.

- Record AEs as described in [Section 8](#).
- The investigator or an authorized designee completes the CRF and updates the investigational product accountability records.
- The investigator or appropriately qualified designee reviews the e-diary data online at frequent intervals (daily is optimal) for the 14 days following vaccination to evaluate subject compliance and as part of the ongoing safety review.

6.1.3. Visit 2 (Month 1; 28 to 35 Days After Vaccination) – Clinic Visit

- Ensure and document that the subject continues to be eligible for the study and that none of the temporary blood draw delay criteria are met.
- Perform a contraception check (see [Section 4.4.1](#)), if applicable.
- Record nonstudy vaccinations and concomitant medications as described in [Section 5.11.3](#).
- **CC1** [REDACTED]
- Collect a blood sample of approximately 50 mL for immunogenicity assessments.
- Review the subject's e-diary data and collect the e-diary. Collect stop dates of any e-diary events ongoing on the last day that the e-diary was completed and record stop dates in the CRF.
- Determine whether any AEs, SAEs, or NDCMCs have occurred since Visit 1 and follow up on any previously reported ongoing AEs, SAEs, or NDCMCs to determine the outcome (ie, record stop dates or confirm if they are still continuing) and record as described in [Section 8](#).
- Remind the subject to contact the investigator or site staff immediately if any significant illness or medical event (eg, emergency room visit or hospitalization) occurs during the study period.
- The investigator or an authorized designee completes the CRF.

6.1.4. Visit 3 (Month 6; 168 to 196 Days After Vaccination) – Telephone Contact

- Record nonstudy vaccinations and medications as described in [Section 5.11.3](#).
- Determine whether any NDCMCs or SAEs have occurred since Visit 2 and follow up on any previously reported ongoing AEs, SAEs, or NDCMCs to determine the outcome (ie, record stop dates or confirm if they are still continuing) and record as described in [Section 8](#).

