7.2.2. Subject Electronic Diary

The subject will be asked to monitor and record local reactions, systemic events, fever, and antipyretic/pain medication used to treat symptoms, each evening for 14 days following vaccination (Day 1 through Day 14, where Day 1 is the day of vaccination) on a system that uses a personal digital assistant (PDA) or other technology. This system, hereafter referred to as the subject's e-diary, allows recording of these assessments only within a fixed time window, thus providing the accurate representation of the subject's experience at that time. Data on local reactions, systemic events, fever, and antipyretic/pain medication used to treat symptoms reported on the e-diary will be transferred electronically to the e-diary vendor, where they will be available for review by investigators, their appropriately qualified designees, and sponsor staff at all times via an internet-based portal. At intervals agreed to by the vendor and Pfizer, these data will be transferred electronically to Pfizer for analysis and reporting.

These data do not need to be reported by the investigator in the CRF. However, if a subject withdraws because of prompted events reported in the e-diary, the event(s) should be recorded on the AE page of the CRF, regardless of whether the investigator considers the event(s) to be clinically significant.

Investigators (or appropriately qualified designees) are required to review the e-diary data online at frequent intervals (daily is optimal) to evaluate subject compliance and as part of the ongoing safety review (see Stopping Rules in [Section 7.2.1](#)).

The investigator or designee must contact the subject in order to obtain stop dates for any reactions ongoing on the last day that the e-diary was completed. The stop dates should be entered in the CRF at Visit 2.

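### The SAP duration rule leaves a known CRF stop date on or before Day 14 unused when the e-diary ends early, so the reaction is cut at its last diary entry

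*SAP*

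**What the plan says.** **SAP 6.1.1, duration from first to last day.** Duration runs from the start of the first reported reaction to the resolution of the last one. Resolution means the final reaction day "recorded in the e-diary if the reaction lasted 14 days or less, or the date the reaction ended if it continued beyond Day 14". Only for the second branch is the CRF named as the source. Two further rules apply: "Days with redness or swelling with diameter <2.5 cm will be excluded", and "If there is no known date when the reaction ended, then duration will be missing (unknown").

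**SAP 6.1.1, total days.** The count is of days with the reported reaction, "including days after Day 14 (if any").

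**SAP 6.1.2** applies the local-reaction rules to systemic events and fever where applicable. **SAP 8.2.1.1** computes duration as last day minus first day plus 1, without naming the source of the last day, and plans both durations for every event.

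**Protocol 6.1.3 (Stage 1, Visit 2) and 6.2.2 (Stage 2, Visit 2)** give the same instruction: "Collect stop dates of any e-diary events ongoing on the last day that the e-diary was completed", with the dates recorded in the CRF. Protocol 7.2.2 repeats that the site must contact the subject to "obtain stop dates for any reactions ongoing on the last day that the e-diary was completed", and that these dates are "entered in the CRF at Visit 2". It also says that the e-diary "allows recording of these assessments only within a fixed time window".

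**The concern.** The two documents use different triggers for the CRF date. The protocol asks whether the event was ongoing at the last completed diary day, whichever day that was. The SAP asks whether the reaction went past Day 14. The two agree when the diary is complete through Day 14. They part when the diary stops earlier with the reaction still present and the reaction then ends on or before Day 14. In that case the site has been told to collect an end date and the SAP rule does not call for it. Because late diary entry is blocked by the fixed window, the CRF date is the only visible record of when the reaction ended.

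The error runs in one direction: it shortens reported durations in a study whose primary objective is to describe safety. SAP 8.1 summarizes continuous variables with, among others, the mean and the maximum, so one cut record can lower a reported maximum if it was the longest in its group.

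**Working it through.** The documents state no duration figure, so there is none to reproduce. The check applies the rule to day patterns.

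**Inputs.** The formula, last day − first day + 1, is from SAP 8.2.1.1. The resolution rule is from SAP 6.1.1. The trigger for the CRF stop date is from protocol 6.1.3, 6.2.2 and 7.2.2. The day patterns, shares and numbers of reporters below are my assumptions. The stop date is treated here as the last day with the reaction.

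**1. Early diary stop: onset Day 2, last entry Day 5, reaction ongoing.**

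| CRF stop | SAP as written | Using the CRF date |
|---|---|---|
| Day 9 | 5 − 2 + 1 = 4 | 9 − 2 + 1 = 8 |
| Day 12 | 4 | 12 − 2 + 1 = 11 |
| Day 14 | 4 | 14 − 2 + 1 = 13 |
| Day 16 | 16 − 2 + 1 = 15 | 15 |

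Two more days of reaction, from a Day 14 stop to a Day 16 stop, add 11 days of reported duration. With the diary complete through Day 14 and a Day 14 end, both columns give 13.

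**2. Range.** Take every pattern with onset ≤ last entry < stop ≤ Day 14. There are C(14,3) + C(14,2) = 364 + 91 = 455. The shortfall is stop − last entry. It runs from 1 to 13 days, sums to 1820, and so has mean 1820/455 = 4.0 and median 3. The patterns are equally weighted, so this is a range and not a forecast.

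**3. Effect on a group mean** = share of reactions cut × days cut, both assumed.

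| Share cut | 1 day | 4 days | 13 days |
|---|---|---|---|
| 2% | 0.02 | 0.08 | 0.26 |
| 5% | 0.05 | 0.20 | 0.65 |
| 10% | 0.10 | 0.40 | 1.30 |

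One record cut by 4 days lowers the mean by 4/10 = 0.40, 4/20 = 0.20 or 4/100 = 0.04 day with 10, 20 or 100 reporters.

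**4. Effect on the maximum, constructed example.** Twenty reactions: four of 1 day, six of 2, five of 3, three of 4, one of 5 and one of 8. The sum is 56, the mean 2.8, the median 2.5 and the maximum 8. If the 8-day reaction is scored 4, the sum is 52, the mean 2.6, the median still 2.5 and the maximum 5.

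**5. Overlap of the branches.** The first branch is defined by length and the second by study day. A Day 5 to Day 16 reaction lasts 16 − 5 + 1 = 12 days and also continues past Day 14, so it meets both. With a complete diary it is 14 − 5 + 1 = 10 days under the first branch and 12 under the second. With onset on Days 1 to 14, 91 onset/end pairs meet both. The first branch probably means that the reaction ended by Day 14.

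**6. Total days.** Suppose the diary shows the reaction on Days 2, 3 and 5 but not Day 4, with last entry Day 5 and CRF stop Day 9. The diary alone gives 3. Adding Days 6 to 9 gives 3 + 4 = 7, but only if all four unobserved days are taken as reaction days. The SAP does not say which applies.

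**The case against.** The best reply is that the sentence was drafted with a completed 14-day diary in mind. Duration is said to run to resolution, and a reaction with an early diary stop can be placed in the first branch only by looking at the CRF date. On that view the SAP is silent about incomplete diaries and a programmer might use the CRF date anyway. It is fair to say that nothing shows an intent to discard the date. But the first branch does name the last diary day as resolution. The missing-duration sentence does not help, since here the end date is known. If two programmers could reach 4 and 8 days from the same record, the text still needs repair.

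It can also be argued that diary data are better inside the 14-day window: they are entered on the day, while CRF dates are entered at Visit 2 and carry no visible size threshold. That stands as a limit on the fix. It does not justify relying on the CRF date after Day 14 and ignoring it before.

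Three stronger readings are tempting, and the documents do not support them:
- **That the total-days rule excludes days between an early diary stop and Day 14.** The text includes days after Day 14 but does not say that only those are added. It is silent on this case.
- **That the SAP can settle what the CRF stop date means.** SAP 6.1.2 and protocol 7.2.3.3 follow a Day 14 fever until one fever-free day in order to collect a stop date, which leaves open whether the last fever day or the fever-free day is entered.
- **That the safety conclusions are biased.** The primary endpoints are proportions, which this rule does not touch, and the same rule applies to both groups.

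**Conclusion.** The concern holds as a defect in a stated derivation rule. As written, SAP 6.1.1 cuts a reaction at its last diary entry when the diary stops early and the reaction ends by Day 14, although the protocol has the end date collected. The shortfall per affected record is 1 to 13 days. The length and study-day branches also overlap and should be reconciled.

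The weight is moderate. Duration is a supporting descriptive summary with no test or decision rule attached. The number of affected records is not known from the documents, and frequent diary review, with daily as the optimum, should keep it small. The effects on means and maxima shown above rest on assumed shares and a constructed set. Redacted text in SAP 6.1.1 may add rules that are not visible. The correction is worth making because it is cheap and the data are already required.

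**What to change.** Replace the resolution sentence in SAP 6.1.1 with wording to this effect:

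> If the reaction was still present on the final completed e-diary day, whether that was Day 14 or earlier, resolution is the CRF stop date. Otherwise it is the last e-diary day with the reaction. For redness and swelling, a diary day counts only at 2.5 cm or more. If the reaction was still present on the final completed diary day and no CRF stop date was obtained, duration is missing.

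This also removes the overlap. Then:
- State in 8.2.1.1 that the last day is this resolution day, for systemic events and fever as well.
- For total days, count the days after the last completed diary day through the CRF stop date on the same basis as days after Day 14, and footnote that these days are assumed continuous.
- Do not redefine the CRF field in the SAP. Check the CRF completion instructions on whether the stop date is the last day present or the first event-free day, and state the matching calculation. For fever on Days 14 and 15 with Day 16 fever-free, the last fever day gives 15 − 14 + 1 = 2 days; using the fever-free day unadjusted gives 16 − 14 + 1 = 3.

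**Cost.** A few lines of SAP text and a merge of CRF stop dates with diary data, with no new collection. The downside is that CRF dates may rest on recall at Visit 2 and may include redness or swelling days below 2.5 cm. Footnote this in the duration tables. The separate durations for reactions of 21 units or more cannot be repaired this way, because no size is visible with the CRF date.
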